NKG2D	Natural killer group 2D (an activating receptor)
NMISS	Number of subjects with missing observations
OR	Odds ratio
PCS	Physical component summary
PD	Pharmacodynamic(s)
PF	Physical functioning
PGA	Physician Global Assessment of Disease
PK	Pharmacokinetic(s)
POC	Proof-of-concept
PP	Per protocol
PRO	Patient reported outcome
PT	Preferred term
PtGA	Patient Global Assessment of Disease
RBC	Red blood cell
RCD-II	Type II Refractory Celiac Disease
RE	Role limitations due to emotional problems
SAE	Serious adverse event
SAP	Statistical analysis plan
sCD3-	Surface CD3-negative
sCD8-	Surface CD8-negative
SD	Standard deviation
SF-12	Short Form 12 questionnaire
SOC	System organ class
TcR	T cell receptor
ULOQ	Upper limit of quantification
UN	Unstructured
VT	Vitality
VH:CD	Villous height to crypt depth ratio
WBC	White blood cell

WHO DD World Health Organization Drug Dictionary

1 Introduction

This is a statistical analysis plan (SAP) for study CELIM-RCD-002 which is based on the final study protocol CELIM-RCD-002 Version 3 (dated 11JUL2016). This SAP describes the statistical analyses which will be presented in the clinical study report.

2 Study objectives and endpoints

The study objectives are the following:

The **primary objective** of the study is:

- To assess the efficacy of AMG 714 in treating Type II Refractory Celiac Disease (RCD-II) in adult patients.

The **primary efficacy endpoint** is:

- The Immunological Response 1, the % of aberrant intraepithelial lymphocytes (IELs) vs total IELs as assessed by flow-cytometry.

The primary endpoint of the study will be evaluated by the relative (%) change from baseline to Week 12 in the % of aberrant IELs vs total IELs between the AMG 714 dose arm and the placebo arm.

The **secondary efficacy endpoints** of the study are:

- Immunological Response 2 (i.e. the % of aberrant IELs vs intestinal epithelial cells [IECs]);
- Histological response – small intestinal villous height to crypt depth (VH:CD) ratio;
- Histological response – Marsh score;
- Histological response – total IEL counts;
- Clinical symptoms (i.e. Bristol Stool Form Scale [BSFS], Gastrointestinal Symptom Rating Scale [GSRs] and celiac disease GSRs [CeD-GSRs]).

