An interim analysis for safety and PK data will be conducted when the tenth randomized subject reaches Visit 4 (Week 4/Day 28; subjects not replaced if dropped out). The interim analysis, specified in more detail in the Data Safety Monitoring Board (DSMB) charter, will be unblinded and performed by an independent DSMB which will also monitor unblinded safety data throughout the study. In addition to safety and PK, other information available at the time of the analysis may be considered and a recommendation to stop, continue or modify the study will be made by the DSMB to the Sponsor. Should the exposure of AMG 714 be below the anticipated range, a root cause analysis will be done, which could result in a protocol amendment. The recommendation and decision will be shared with the investigational sites and ethics committees. No adjustments in significance levels will be applied to the final analyses as this interim assessment is DSMB-driven for the purpose of safety assessments and to assure that minimal steady-state exposures (10 $\mu\text{g/mL}$) are achieved. No efficacy data will be assessed during this interim analysis.

5 Randomisation

Randomisation, i.e. the random allocation of treatments to subject numbers, will be performed according to the design of the study. A detailed description of the randomisation method, including the size(s) of randomly permuted blocks used to balance the randomisation, will be stored at the restricted area of StatFinn server, where only the randomization expert and the unblinded statistician will have access to. Once the data base is locked and the treatment code open, the randomization documents will be moved to the non-restricted area.

Subjects will be randomized at a 2:1 allocation ratio to receive 8 mg/kg AMG 714 or placebo for a total of 7 administrations over 10 weeks. The randomization will not be stratified since

this is the first-ever placebo controlled randomized clinical trial in RCD-II and there are no known confounding factors for response to treatment.

6 Statistical hypotheses

The primary endpoint of the study is the Immunological Response 1: relative (%) change at Week 12 in the % of aberrant IELs vs total IELs as assessed by flow-cytometry between the AMG 714 dose arm and the placebo arm.

The primary endpoint of Immunological Response 1 will be tested as follows:

$$H_0: \mu_{AMG\ 714} = \mu_{placebo}$$

against the alternative

$$H_1: \mu_{AMG\ 714} \neq \mu_{placebo}$$

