where $\mu_{AMG\ 714}$ and $\mu_{placebo}$ denote the mean baseline to Week 12 relative (%) change in % aberrant IELs vs total IELs as assessed by flow-cytometry in the AMG 714 and placebo arm, respectively. The hypotheses will be tested using a two-sided, 0.10 level of significance.

7 Estimation of sample size

The CELIM-RCD-002 study is an exploratory proof-of-concept (POC) study of an experimental medication, AMG 714, in RCD-II patients. While it will be the first such study sponsored by a pharmaceutical company, the straightforward design is based on several academic studies (Goerres *et al*, 2003; Brar *et al*, 2007; Tack *et al*, 2011a, 2011b) as well as on the nonclinical proof-of-principle signal obtained with AMG 714 in intestinal explants from patients with RCD-II (Malamut *et al*, 2010).

The sample size is based on the size of previous academic studies. Published prospective academic studies have ranged from 13 to 18 subjects total (Tack *et al*, 2011a, 2011b) and CELIM-RCD-002 will be the largest prospective trial ever conducted in RCD-II, a very rare malignant disease.

The sample size of 24 subjects (16 subjects in AMG 714 arm and 8 subjects in placebo arm) has been calculated to achieve at least ~ 80% power to detect a 20 percentage point difference in the primary endpoint, the difference in the baseline-to-Week 12 reduction of % aberrant IELs vs total IELs between the AMG 714 arm and placebo arm.

This sample size calculation was based on the following assumptions:

- Two-sided type one error rate $\alpha = 0.1$.
- Power $1-\beta = 0.8$.
- Analysis method: one-way analysis of variance (ANOVA) by SAS[®] (proc power).
- 2:1 allocation ratio between the AMG 714 and placebo arms.
- Common SD = 17.4 for the baseline to Week 12 reduction in % aberrant IELs as assessed by flow-cytometry.

- Mean change of 20 percentage points and 0 percentage points in the baseline to Week 12 reduction in % aberrant IELs in the AMG 714 and placebo arms, respectively.

The standard deviation used for the sample size calculation is computed from the % aberrant IELs (obtained by flow-cytometry) data from 13 subjects treated with cladribine (subset of the subjects reported in Tack et al, 2011).

8 Statistical methods

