8.2.1 Definition of derived variables

Geometric mean will be calculated as:

$$\text{mean}_{\text{geo}} = \exp\left\{\frac{1}{n} \sum_{i=1}^n \ln x_i\right\}.$$

Values that are missing or not available will be ignored in calculation of geometric mean.

CV%_{geo} will be calculated using the following formula:

$$\text{CV}\%_{\text{geo}} = 100\% \cdot \sqrt{\exp V_{\ln} - 1}.$$

Values that are missing or not available will be ignored in calculation of CV%_{geo}.

Absolute change from baseline for a given treatment needs to be calculated, the following formula will be used:

$$\text{Absolute change from baseline} = \text{Post-baseline value} - \text{Pre-dose value}.$$

For weekly scores, Week 0 score is considered to be the baseline value. If Week 0 score is not available, the first non-missing result within 2 weeks of treatment will be used as baseline. For daily scores (e.g. CeD PRO), Day 0 score is considered to be the baseline; in case Day 0 score is not available, the first non-missing result within 2 weeks of treatment will be used as baseline. Otherwise, the given subject will be considered non-evaluable for the specific test. In case pre-dose value doesn't exist (i.e. for biopsy endpoints), screening value will be used as baseline.

In the case where relative (%) change from baseline needs to be calculated, the following formula will be used:

$$\text{Relative (\%) change from baseline} = (\text{Post-baseline value} - \text{Pre-dose value}) / (\text{Pre-dose value}) \cdot 100\%.$$

For weekly scores, Week 0 score is considered to be the baseline value. If Week 0 score is not available, the first non-missing result within 2 weeks of treatment will be used as baseline. For daily scores (e.g. CeD PRO), Day 0 score is considered to be the baseline; in case Day 0 score is not available, the first non-missing result within 2 weeks of treatment will be used as baseline. Otherwise, the given subject will be considered non-evaluable for the specific test. In case pre-dose value doesn't exist (i.e. for biopsy endpoints), screening value will be used as baseline.

Body mass index (BMI) is calculated using the formula:

$$\text{BMI (kg/m}^2\text{)} = \text{weight (kg)} / [\text{height (m)} * \text{height (m)}].$$

Body surface area (BSA) is calculated using Dubois' formula:

$$\text{BSA (m}^2\text{)} = 0.007184 * \text{height (cm)}^{0.725} * \text{weight (kg)}^{0.425}.$$

Table 2 Decimal places for summary statistics of continuous and categorical variables

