8.6 Analysis of efficacy

8.6.1 Primary efficacy variable

Primary efficacy endpoint of the study is:

- Immunological Response 1: Relative (%) change from baseline to Week 12 in the % of aberrant intestinal intraepithelial lymphocytes (IELs) vs total IELs as assessed by flow-cytometry.

The primary endpoint will be analysed using analysis of covariance (ANCOVA), where the baseline % aberrant IELs vs total IELs will be included as a covariate and treatment group as a fixed effect in the statistical model.

The analysis of the primary endpoint will be carried out using the PP population. Subjects having Week 6 biopsy data who are lost to follow-up for further visits will have their Week 6 value carried forward for the final analysis (more details available in *Chapter 8.2.2 Missing values*).

The following model will be fitted:

$$Y_{ij} = \mu + \beta \cdot \text{baseline \% IEL vs total IEL}_{ij} + \alpha_j + \varepsilon_{ij},$$

where

Y_{ij} is the relative (%) change from baseline in the % of aberrant IELs vs total IELs for subject i ($i = 1, \dots, n_j$) from treatment group j ($j = 1, 2$),

μ is the overall mean,

β is the parameter estimate of baseline % IELs vs total IELs,

α_j is the fixed effect due to treatment j ,

ε_{ij} is the random error for subject i from treatment group j ; $\varepsilon_{ij} \sim N(0, \sigma_\varepsilon^2)$.

The following SAS code will be used to fit the above-specified model (NOTE: SAS codes provided in this document may be modified based on statistical considerations, without requiring SAP amendment):

```
proc glm data=IELt alpha=0.1 outstat=F_tests;
  class trt;
  model IELt_change = bl_IELt trt / clparm solution SS1 SS2;
  estimate "AMG 714 vs Placebo" trt 1 -1;
  lsmeans trt /cl stderr alpha=0.05;
  ods output ParameterEstimates=Par_est LSMeanCL=LS_meanCL
             LSMeans=LS_mean OverallANOVA=ANOVA Estimates=Eff_est;
run;
```

The modelling results (ANOVA table, parameter estimates, estimated treatment effect, marginal (i.e. least squares) means estimates and results of the check of assumptions) will be tabulated and 90% confidence intervals added, where appropriate.

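### The SAP's only power figure is for percentage-point change in aberrant IELs, but its primary test is on relative (%) change, for which no effect size, SD or power is given

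*SAP*

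**What the plan says.** **Sizing.** SAP section 7 states that the sample size "has been calculated to achieve at least ~ 80% power to detect a 20 percentage point difference in the primary endpoint". The assumptions listed there include "Mean change of 20 percentage points and 0 percentage points in the baseline to Week 12 reduction in % aberrant IELs" for AMG 714 and placebo respectively, a common SD of 17.4 for that reduction, two-sided alpha 0.10, 2:1 allocation and one-way ANOVA. The SD was "computed from the % aberrant IELs (obtained by flow-cytometry) data from 13 subjects treated with cladribine". Protocol section 22.1 has the same inputs and adds that drop-outs are not allowed for.

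**Primary endpoint in the SAP.** Section 2 says the endpoint "will be evaluated by the relative (%) change from baseline to Week 12 in the % of aberrant IELs vs total IELs". Section 6 defines it as "relative (%) change at Week 12 in the % of aberrant IELs vs total IELs as assessed by flow-cytometry", and the two means in the hypotheses "denote the mean baseline to Week 12 relative (%) change in % aberrant IELs vs total IELs as assessed by flow-cytometry". Section 8.6.1 names the same variable, "Relative (%) change from baseline to Week 12 in the % of aberrant intestinal intraepithelial lymphocytes (IELs) vs total IELs", and makes it the ANCOVA response. Section 8.2.1 gives the definition: post-baseline minus pre-dose value, divided by the pre-dose value, times 100. Section 8.6.1 then fits the same model to absolute change, as a secondary assessment.

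**Primary endpoint in the protocol.** Section 22.5.1 tests the mean reduction in % aberrant IELs. It does not call this relative, and section 22.1 expresses it in percentage points.

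**The concern.** A difference of 20 percentage points in a variable that is itself a percentage, with an SD taken from values of that variable, reads naturally as absolute change. The protocol is consistent on that reading. The SAP moves the primary test to relative change but keeps the protocol's sizing text, including the claim that the calculation concerns the primary endpoint. The only power figure is then attached to a test for which it was not computed.

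Two things are at stake. If the primary result is null, a reader may cite roughly 80% power that nobody calculated for that test. And a reader of the protocol and a reader of the SAP may come away with different scales for the one formal primary hypothesis.

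**Working it through.** **1. Reproduce the stated figure.** Inputs from SAP section 7: difference 20, SD 17.4, n = 16 and 8, two-sided alpha 0.10. One-way ANOVA on two groups is the two-sample t test.

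- Standard error = 17.4 × √(1/16 + 1/8) = 17.4 × 0.4330 = 7.534
- Noncentrality = 20 / 7.534 = 2.654, on 22 df
- Power (noncentral t) = 0.823

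At 14:7 the power is 0.773, so 24 is the smallest exact 2:1 size that reaches 80%. The arithmetic is right for the inputs given.

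**2. What the relative scale would need.** Power depends only on difference/SD. The plan's ratio is 20/17.4 = 1.149; at 16:8, 80% power needs at least 1.111. The largest SD that still gives 80% is therefore difference/1.111:

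- relative difference 40: SD up to 40/1.111 = 36.0
- relative difference 21: SD up to 21/1.111 = 18.9

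Neither the difference nor the SD is given on this scale.

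**3. Why the figure does not convert.** A 20-point fall is 100 × 20/B percent of baseline B: 100% at B = 20, 40% at 50, 21% at 95. If every subject had the same baseline, the SD would rescale by the same factor (at 50: difference 40, SD 34.8) and power would stay 0.823. Entry requires more than 20% aberrant IELs by flow cytometry (or more than 50% by immunohistochemistry) and sets no upper limit, so baselines can differ widely. The ratio is then no longer preserved.

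**4. Illustration.** The documents give no baseline distribution, so the uniform ranges below are assumptions and the results are not bounds. Design: 16:8, no drop-outs, 40,000 simulated trials per cell, post-values clipped to 0–100, ANCOVA with baseline as covariate (21 df), two-sided alpha 0.10. Each cell shows power on absolute / relative change; Monte Carlo standard error is about 0.002.

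| Baseline range | (a) Constant 20-point effect, noise SD 17.4 | (b) Effect proportional to baseline (mean 20), noise SD 17.4 | (c) Effect and noise both proportional |
|---|---|---|---|
| 50–95 | 0.800 / 0.787 | 0.796 / 0.764 | 0.801 / 0.806 |
| 40–90 | 0.803 / 0.785 | 0.797 / 0.749 | 0.804 / 0.816 |
| 25–80 | 0.807 / 0.782 | 0.799 / 0.711 | 0.810 / 0.834 |
| 20–95 | 0.802 / 0.758 | 0.788 / 0.638 | 0.802 / 0.843 |

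In (c) the noise has root mean square 17.4. Clipping trims the realised absolute difference to 18.6–19.5 points.

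The missing inputs would look like this: under (a) with baselines 40–90, the mean relative difference is 31.4 and the within-arm SD before covariate adjustment is 28.6.

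**5. The other reading of 20.** Suppose the target were a 20% relative fall while SD 17.4 remained in absolute points. With a single common baseline, power would be 0.36 at 50 (a 10-point fall), 0.61 at 75 (15 points) and 0.75 at 90 (18 points). If the 17.4 were also relative, power would again be 0.823. The text does not show how 17.4 was derived in enough detail to rule this out, so this reading needs clarification too.

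**The case against.** The strongest reply is that no material loss is shown. In the scenario closest to the stated inputs, a constant 20-point effect, relative-scale power is 0.76–0.79 against 0.80–0.81 on the absolute scale, for a plan that claims only about 80%. With proportional effect and noise the relative scale does slightly better. The low value of 0.64 needs a wide assumed baseline range and a particular noise model. All of this stands, and it is why the point is about an unstated power, not an underpowered trial.

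The analysis that was sized also survives, as the secondary ANCOVA on absolute change. The sizing sentence goes on to describe its quantity as the baseline-to-Week 12 reduction, so a careful reader can see what was powered. Both documents say the sample size also follows earlier academic studies in a very rare disease. Protocol section 13.1 calls the study positive for go/no-go purposes if either immunological response is positive. These facts lower the consequences; they do not make the power statement true of the test it names.

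Finally, protocol section 22.5.1 says only reduction and fixes no unit, and protocol section 22 leaves detailed methodology to the SAP. Choosing relative change can be read as that delegated detail. This weakens any claim of a flat contradiction between the documents. It does not help SAP section 7, which sits directly after a hypothesis stated in relative terms.

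**Conclusion.** The concern holds. The sample size is correctly computed for absolute percentage-point change (0.823 at 16:8, no drop-outs), but SAP section 7 attributes that power to a primary endpoint that the rest of the SAP defines as relative change. No relative-scale difference, SD, baseline distribution or power appears in either document.

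The size of the error cannot be fixed from the documents. Under the assumed baselines, relative-scale power ran from 0.64 to 0.84, so it may be lower than, similar to or higher than the stated figure. The conclusion rests on the natural reading of 20 percentage points as absolute change; on the alternative reading the section is still unclear about its target.

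This should be corrected, but the harm is limited: the 90% interval on the primary scale and the absolute-change model will still show which effects a result excludes.

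**What to change.** In SAP section 7:

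1. State that the ~80% (0.823 by one-way ANOVA, 16:8, no drop-outs) applies to absolute percentage-point change and not to the primary test on relative change.
2. Add a target difference, SD and power for relative change under stated assumptions. The 13-subject cladribine data would serve if individual baselines are available; otherwise show a range.

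These two items cost one paragraph, with no new data and no change to the sample size, model or alpha. The sponsor must accept that the relative-scale figure may fall below 80%.

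3. Reconcile the primary scale between protocol sections 22.1 and 22.5.1 and SAP sections 2, 6 and 8.6.1, and record the reason for the choice.

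Item 3 is more than wording. Keeping relative change means aligning the protocol, most plainly by an amendment, since section 22.1 now reads in percentage points. Making absolute change primary would need a new version of a SAP already final at version 2.0 and would give up the scale the sponsor chose. It is open only if decided before unblinding. Items 1 and 2 are worth doing whichever way item 3 is settled.

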8.1 Data sets to be analysed

The populations for analysis will be the intention to treat (ITT, safety population, at least one dose of the investigational product received) and the per protocol population (PP, efficacy, i.e., available and evaluable pre- and post-biopsy information [Week 6]).

PP population: the PP population will exclude non-evaluable subjects and subjects with major protocol deviations thought to impact the ability to assess the effect of treatment. The PP population will also exclude atypical RCD-II patients (patients with a different phenotype of the aberrant IELs) for the purpose of analysis of Immunological Response 1 and 2; however, they will be included in all other efficacy assessment where a sensitivity analysis maybe performed excluding these subjects if these subjects are determined to be influential. Exclusion of subjects from the PP set will be reviewed, documented and approved before the study is unblinded to the study Sponsor.

Non-evaluable subjects will include subjects missing one of the two biopsies (or with biopsies of insufficient quality to generate valid data as determined by the Sponsor prior to database lock) and subjects dropping out of the study before Week 6. If a discontinuation occurs on or after Week 6 and the second biopsy is collected, then the subject is considered evaluable.

Atypical patients may also be analysed as a separate population if the results and sample size suggest such analysis is valuable.

The following major protocol deviations, as determined by the Sponsor prior to database lock, will lead to exclusion of subject from the PP population and will be thoroughly documented in the clinical study report:

- Intake of any forbidden concomitant medication or participation in other medical procedures, in case there is reason to believe, by the judgement of the Sponsor or investigator, that such concomitant medication/procedures would have a significant effect on the efficacy data obtained;
- Significant deviations from the inclusion/exclusion criteria of the study not previously approved by the Sponsor and determined prior to database lock to have impact on interpretation of results.

ITT (safety) population: this population consists of all randomized subjects who have received at least one dose of the study drug. The safety population is by definition the same as the ITT population. If a subject had a misallocated treatment on a specific visit, observed upon unblinding, a secondary sensitivity analysis will be performed on as treated basis.

Main efficacy measures which require pre- and post-treatment biopsies will be analysed using the PP population (at least 2 biopsies, the second on Week 6 or later). Continuous efficacy variables will be analysed based on the ITT population. Demographic and baseline variables will be assessed using both ITT and PP populations. Safety parameters will be analysed using the ITT population. Compliance data will be reviewed to assure subjects were treated as randomized.

A detailed description of the study populations and subjects included will be given in the Subject Classification Document, which will be finalized before the database lock.

Table 1 Data sets to be used in the analysis

Primary variable ²	Secondary variables ^{1,2}	Exploratory/PD variables ¹	Safety variables	Demographic and baseline variables
PP	ITT PP	ITT PP	ITT	ITT PP

¹PP set used for biopsy-dependant variables and ITT for all other variables.

²PP population will exclude atypical RCD-II patients (patients with a different phenotype of the aberrant IELs) for the purpose of analysis of Immunological Response 1 and 2.

